1.0 Introduction

1.1 Background

Research evidence has shown that the symptoms of chronic pain, anxiety, depression, and sleeplessness, or any combination of these symptoms are prevalent among patient populations with chronic medical conditions, particularly inflammatory arthritis (Psoriatic Arthritis, Rheumatoid Arthritis), Fibromyalgia, anxiety disorders (PTSD, Generalized Anxiety Disorder), Depression, Chronic Pain conditions (neuropathy, chronic neck and back pain, Osteoarthritis, TMJ Syndrome), and sleep disorders. Patients with one of these chronic conditions often have clusters of one or more of these four symptoms (pain, anxiety, depression, and/or sleeplessness).

These patient populations have a need for an innovative treatment approach to address these symptoms, as they often occur simultaneously. By addressing all possible combinations of these symptoms in an individual patient or population, significant improvements in patients' health and health outcomes can be achieved.

Globally, the lifetime prevalence of anxiety disorders from a 2013 meta-analysis was 7.3% (4.8-10.9%) and ranged from 5.3% (3.5-8.1%) in African cultures to 10.4% (7.0-15.5%) in Euro/Anglo cultures.¹ These statistics translate into 1 out of 13, and 1 out of 10 people affected globally and in North America, respectively. In the United States alone, anxiety affects about 18% of the population or 40 million adults aged 18 and older at cost of more than \$42 billion a year in 1990.^{2,3}

In a separate systematic review on depression, the global prevalence of major depressive disorder was 4.7% (4.4-5.0%).⁴ In 2015, over 16 million adults aged 18 or older have been estimated to have had at least one major depressive episode in the prior year, representing 6.7% of all U.S. adults.⁵

Insomnia is a global public health issue and is believed to affect approximately 30-35% of the global population.^{6,7} Poor sleep has been associated with decreased immunity, depression, anxiety, poorer quality of life, obesity, increased pain, occupational errors, absenteeism from work, and motor vehicle crashes.^{7,8}

The prevalence of chronic pain, like all the previous conditions discussed, is highly variable among subgroups in population and by indication. It is estimated that approximately 20% of the adult European population suffers from chronic pain.⁹ Similarly, approximately 17.6% (about 40 million) of US adults experience severe levels of pain along with over 11.2% (25.3 million) of adults suffering from daily pain for the prior 3 months at an annual estimated cost of approximately \$560-\$635 billion.^{10,11}

Given the high prevalence of conditions associated with chronic pain, anxiety, depression, and/or sleeplessness (CPADS), the associated economic burden, and lack of safe and cost-effective therapies, interest and research is expanding into the field of neuromodulation therapies, including TENS devices, to meet this need.

The Nu-V3 device is not considered to be a Transcutaneous Electrical Nerve Stimulation (TENS) device. TENS devices are applied only in the area of the body directly related to the pain. The Nu-V3 device is placed on the auricular (ear) area and utilizes a non-invasive electrical micro-signal to access the cranial nerves via three small electro-gel pads. There are no TENS devices currently approved or cleared by the FDA that qualify as being substantially equivalent.

Under further research pertaining to accessing the cranial nerves, in particular the vagus nerve, we discovered that there are a variety of Vagal Nerve Stimulators available. However, none are non-invasive and small enough to be attached to the ear while stimulating multiple cranial nerves in the auricular area.

In summary, while Nu-V3 is technically a transcutaneous device, the mechanism for mitigation of symptoms (chronic pain, anxiety, depression, and sleeplessness) is unique by TENS standards for the following reasons:

- A. TENS is typically placed in the general area where the pain exists. Nu-V3 is placed only in the auricular area (on the ear) and accesses the cranial nerves as the mechanism for relief.
- B. TENS devices are known to stimulate muscular tissue and nerves in the area where pain exists, creating vasodilation (increased blood flow) and thereby the possibility of temporary relief. Nu-V3, by accessing the cranial nerves (specifically the vagus nerve) non-invasively, acts to stimulate the body's natural enkephalins and elevate blood flow, and may result in the balancing or rebalancing of the Autonomic Nervous System (ANS).¹²⁻¹⁸
- C. By accessing the cranial nerves in the manner described above, the effect may be cumulative and residual and offer the patient immediate, intermediate, and longer lasting relief from their symptoms.

In part, the purpose of this clinical study is to demonstrate the effect of the device upon the four specific symptoms of chronic pain, anxiety, depression, and sleeplessness. Any one or combination of these symptoms may result in Autonomic Nervous System dysfunction.

1.2 Device Description

The Nu-V3 device is a miniaturized, wearable, microchip-controlled, cranial nerve stimulation treatment device which delivers pulsed micro-signals over a period of 14 days. The Nu-V3 device provides a continuous flow of intermittent, low frequency electrical pulses to the ear's specific cranial nerve endings. The Nu-V3 device is a patent pending, non-invasive transcutaneous stimulating device which offers useful features to the patient and clinical professional. The Nu-V3 device control features are set by the manufacturer and prevent patient misuse of the device.

Three miniature, non-invasive, electro-gel pads are utilized to deliver a micro signal at 1

Hz in a square plus minus waveform, which cycles on and off every three hours to provide a resting period and prevent adaption to the stimulation. The device is powered by three (No.10) zinc air batteries at 1.4 volts each (4.2 volts in total), to provide the required stimulation for up to 14 days. The low frequency, reliability of the zinc air batteries and consistency of the micro-signal through the eight-pin micro-chip technology, provides consistent and equivalent stimulation energy regardless of individual skin impedance.

1.3 Non-significant Risk Medical Device Study

The FDA considers other microcurrent transcutaneous devices (such as TENS devices) as nonsignificant risk devices for medical device studies.¹⁹ The Nu-V3 device used in this study reflects an investigational device that meets the definition of a nonsignificant risk device per review of the IRB.

2.0 STUDY OBJECTIVE

The objective of this research study is to collect data which demonstrates the ability of the Nu-V3 device to offer relief from one or more of the following symptoms: chronic pain, anxiety, depression, and/or sleeplessness.

3.0 STUDY PARTICIPANT SELECTION CRITERIA

3.1 Inclusion Criteria

- Participant is at least 18 years of age
- Participant presents with one or more of the following symptoms: chronic pain, anxiety, depression, and/or sleeplessness
- Participants must score greater than or equal to a 5/10 for their primary symptom score on the Baseline Symptom Questionnaire
- Patient's chosen primary symptom must have an available accrual slot for the participant. If patient scores greater than or equal to a 5/10 for a second symptom, they can be selected to accrue to another symptom slot.
- Participant has signed the Informed Consent Form

3.2 Exclusion Criteria

- Participants with a hearing aid
- Participants with a pacemaker
- Participants with irregular heart rate or a heart rate lower than 60 beats per minute (bradycardia)
- Have had a transplant within the last 2 years
- Have had a heart attack or cardiac bypass surgery within the last 12 months
- Patients with complaints of dizziness or lightheadedness within the last 3 months
- Women who are pregnant

- Participants with Diabetic Retinopathy
- Current ear infection
- SBP < 100 and/or DBP < 60
- History of uncontrolled bipolar disorder within the last 12 months
- History of uncontrolled seizures within the last 12 months
- History of aneurysms
- History of syncope within the last 12 months
- Participants that have had a TIA or stroke within the last 12 months
- Participants with health problems deemed at risk for the study by the Principal Investigator
- Participants with any changes to Pain/Anxiety/Depression/Sleeplessness medications within last 60 days (participants that do not meet this medication-change washout period may be delayed until 60-day period is met)
- Participants that are currently under adjudication process for disability support, VA or other

4.0 STUDY PROTOCOL

The Nu-V3 Clinical Study is a randomized, open-label study using the Nu-V3 cranial nerve stimulation treatment device in patients with chronic pain, anxiety, depression, and/or sleeplessness. Study participants are those who have signed the informed consent form, met the inclusion and exclusion criteria, and are enrolled in the study at one of multiple sites.

Subjects randomized to receive the Nu-V3 treatment will undergo the following regimen:

- At the baseline visit, patients will be asked to complete study questionnaires (Appendix 11) regarding all of the following symptoms: chronic pain, anxiety, depression, and/or sleeplessness, as well as their quality of life, active medications, medical history, and demographical information. The subject's primary symptom of concern will also be notated at baseline, for later assessment of continuation after week 12.
- At each subsequent visit, patients will be asked to complete study questionnaires regarding all the following symptoms: chronic pain, anxiety, depression, and/or sleeplessness, as well as their activity level and quality of life.
- The sessions will begin with the Nu-V3 device being clipped on the ear and three small pads (non-invasive) adhered to the surface of the ear. Each Nu-V3 device lasts for up to 28 days with a change in the pads approximately 7 days into the treatment.
- Each session takes approximately 15-20 minutes. The placement of the device takes approximately 5 minutes, and the remaining time is spent verifying ePRO form completion, and evaluating the patient for all device effects.
- The Nu-V3 device is mobile and is worn externally on the left ear 24 hours a day during treatment, fitting comfortably behind the ear. An electrical signal is sent to

the external ear through coated wire leads attached to the device and adhesive pads which attach to three sites on the ear.

- Participants should be able to perform their typical day-to-day activities while wearing the device. They may shower while wearing the Nu-V3 device, if they do not get the device wet and use the small disposable ear covers that are provided for them.
- In the event the Nu-V3 gel pads are inadvertently removed or the device comes off, the participant will contact the site coordinator. The participant is encouraged to adjust the device placement as needed for comfort.
- Patients should not change their existing forms of treatment or medications without discussion with the study investigator.

Subjects randomized to the observation control arm of the study will undergo the following regimen:

- At the baseline visit, patients will be asked to complete study questionnaires (Appendix 11) regarding all the following symptoms: chronic pain, anxiety, depression, and/or sleeplessness, as well as their quality of life, active medications, medical history, and demographical information. The subject's primary symptom of concern will also be notated at baseline.
- At each subsequent visit, patients will be asked to complete study questionnaires regarding all the following symptoms: chronic pain, anxiety, depression, and/or sleeplessness, as well as their activity level and quality of life.
- Patients should not change their existing forms of treatment or medications without discussion with the study investigator.
- At completion of 12 weeks of standard of care treatment post study enrollment, observation (control arm) subjects will be offered a crossover into the treatment arm of the study for an additional 24 weeks.

Sample size

For this Phase II study, a total of 100-200 subjects will be randomized 1:1 to either the Nu-V3 treatment arm or to the observation treatment arm (SOC, control).

Recruitment

Participants are enrolled into relevant symptom cohorts based on their chronic pain, anxiety, depression, and/or sleeplessness symptom presentation at baseline and treated with the Nu-V3 device for 24 weeks.

Analyses

Interim analysis of reported data will be based on baseline symptom cohort and conducted at 6, 12, 18, and 24 weeks during this time. The participant will be evaluated after the initial 12-week treatment period to assess for further therapeutic need. Upon having three consecutive weeks of mean symptom reduction of $\geq 70\%$ via patient reported numerical scales, the participant will continue as described in the study assessments table, but without device therapy. Then if the participant's primary

symptom score increases at any time by $\geq 20\%$, they may again continue device therapy until week 24, as depicted in section 4.1.

Study subjects randomized to the observation arm will be offered the opportunity to cross-over to the Nu-V3 study treatment arm upon completion of the initial 12-week observation study period.

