5.0 DATA COLLECTION AND RETENTION

The study endpoints data will be collected from each participant's study questionnaires. The data will be collected electronically via the patient's own device and uploaded to an electronic data capture system. The data will be used to measure whether the Nu-V3 device provides participants with a reduction in participants' chronic pain, anxiety, depression, and/or sleeplessness.

The data analysis will include baseline data for each participant's questionnaire prior to beginning treatment with the Nu-V3 device. Longitudinal data will consist of participant's weekly questionnaires measuring chronic pain, anxiety, depression, and sleeplessness during the treatment phase. The final data collection will be completed by participants at the end of the treatment with the Nu-V3 device and will measure chronic pain, anxiety, depression, and sleeplessness.

The Principal Investigator at each site will be responsible for recording, collecting, and storing the research participant's study data. The written records will be stored in a secure location. Only the Principal Investigator or designated study staff will have access to the study records and all electronic files will be password protected. The Principal Investigator will also maintain adequate records for the study including:

- all correspondence with the IRB and Sponsor
- other pertinent data related to the study

All records are to be retained by the Principal Investigator for a period of three (3) years following the closure of the study. Following study closure, the Principal Investigator shall inform Nu-Life of the location of study records and storage changes (i.e., the Principal Investigator leaves the institution where the study was conducted). In such cases, the study records may be transferred to another institution, investigator, or to Nu-Life upon written agreement between the Principal Investigator and Nu-Life.

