8.0 STUDY ENDPOINT and DATA ANALYSIS

8.1 Primary Endpoints: Primary endpoints consisted of the following:

Safety: At screening/baseline, a medical history will be obtained to capture relevant underlying conditions. The screening/baseline examinations will include BP, and HR. Baseline signs and symptoms are those that are assessed within 14 days prior to week 1 treatment.

Concomitant medications will be collected from within 14 days prior to enrollment through the study treatment period and maintenance period (see Study Assessments Table section 4.1).

The primary safety endpoint is the occurrence of reported unanticipated problems involving risk to subjects or others (“UPIRTSOs”). These UPIRTSOs are defined as those problems which alter the risks to subjects or others. This includes any study suspensions or holds. The primary safety endpoint analyses will be based on a risk-benefit conclusion.

Effectiveness: There are four instruments measuring participant’s symptoms of chronic pain, anxiety, depression, and sleeplessness. The primary effectiveness endpoint is a statistically significant reduction in one or more of measures of: chronic pain, anxiety, depression, or sleeplessness between baseline and 12 or 24 weeks after initiating treatment.

The null hypothesis to disprove is that there is no statistically significant reduction from baseline to 12 or 24 weeks in mean chronic pain, anxiety,

depression, or sleeplessness symptom severity scores using the Nu-V3 device compared with the usual care cohort.

The instruments used in this study are:

Chronic Pain – Pain intensity (P), interference with enjoyment of life (E), and interference with general activity (G) (PEG Scale),

The PEG is a three-item instrument that measures pain intensity (one item) and pain interference (two items). Each item is valued from 0 (no pain/interference) to 10 (as bad as you can imagine). The instrument score is calculated as the average of the three item values.

Anxiety - Generalized Anxiety Disorder 7-item (GAD-7)

The GAD-7 is a seven-item instrument that measures respondents' symptoms of anxiety. Each item is scored on a four-point Likert scale, and values range from 0 ("Not at all") to 3 ("Nearly every day".) Items are summed to determine the instrument's score. Values of 10 or higher have been associated with moderate anxiety, while values of 15 or higher have been associated with severe anxiety.

Depression - Patient Health Questionnaire (PHQ-9)

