The PHQ-9 is a nine-item instrument that measures depression-related symptoms and functional impairment. Each item is scored on a four-point Likert scale and values range from 0 ("Not bothered at all") to 3 ("Bothered nearly every day.") The items' values are summed to determine the instrument's score. PHQ-9 values of 10 and 15 represent moderate and moderately severe depression respectively.

Sleeplessness - PROMIS short form 4a

This eight item instrument measures sleep disturbance and sleep-related impairment.

8.2 Secondary Endpoints: Secondary endpoints consisted of the following:

Effectiveness: There are two secondary effectiveness endpoints:

1. In the Nu-V3 device treatment arm, the study will report the mean time from treatment initiation to reduction of symptoms of at least 30% in any of the four domains of symptom measurement.
2. In both the Nu-V3 device treatment arm and the observation arm, the study will report the mean percentage change in symptoms severity from initiation to 12 and 24 weeks for each instrument.

Additional secondary endpoints of this study are:

- Mean improvement in quality of life measured with Patient's Global Impression of Change (PGIC) between the treatment and usual care arm, and

- Mean improvement in activities of daily living via Perceived Treatment Benefit Form (PTB-6) between the treatment and usual care arm.

8.3 Sub-Analyses: Sub-Analyses consist of the following:

The study has several sub-analyses. They include:

- The mean number of weeks that chronic pain, anxiety, depression, and sleeplessness response are achieved and sustained, without utilization of another device or change in other treatments, during the full 24-week intervention in the Nu-V3 device treatment arm.
- The mean number of weeks to initial benefit from Nu-V3 device use in the Nu-V3 device treatment arm. Benefit is defined as a reduction of at least 30% of symptoms in at least one of chronic pain, anxiety, depression, or sleeplessness.
- **The device's comfort-of-use, and patient's perceived treatment benefit** in the Nu-V3 device treatment arm.

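### The primary comparison with usual care is stated at 12 or 24 weeks, but every control is offered the device at week 12 and no untreated control data are scheduled after that

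*Protocol*

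**What the plan says.** **Crossover.** Section 4.0 states it twice. In the control regimen, "observation (control arm) subjects will be offered a crossover into the treatment arm of the study for an additional 24 weeks". Under Analyses, controls "will be offered the opportunity to cross-over to the Nu-V3 study treatment arm upon completion of the initial 12-week observation study period". The offer goes to all controls.

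**Follow-up.** The device-arm tables in section 4.1 cover weeks 1 to 24. The control table covers weeks 1 to 12 only. Neither a control who declines the crossover nor one who accepts it has a control-arm visit after week 12.

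**Primary effectiveness endpoint.** Section 8.1 defines it as a reduction "between baseline and 12 or 24 weeks after initiating treatment". The null hypothesis that follows is again set at 12 or 24 weeks and concerns "symptom severity scores using the Nu-V3 device compared with the usual care cohort".

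**Baseline.** Section 5.0 says the analysis will include "baseline data for each participant's questionnaire prior to beginning treatment with the Nu-V3 device".

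**Secondary endpoints.** Section 8.2 item 2 reports percentage change to 12 and 24 weeks in both arms. Item 1 and the section 8.3 sub-analyses are summaries of the device arm alone.

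**The concern.** A comparison with usual care needs people still on usual care at the time point compared. The protocol names 24 weeks as one of two time points for its primary contrast, yet its own design removes the untreated control at week 12.

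The wording then leaves the place of post-crossover data open. The contrast is described by use of the device and by a usual care cohort, not by randomised allocation. The endpoint is timed from the start of treatment, and controls are said to move into the treatment arm. A crossed-over control could therefore be usual care in weeks 1 to 12 and a device user afterwards.

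At stake is whether a 24-week result can be presented as controlled evidence. In an open-label trial there is also the risk that the choice of contrast is made after results are seen.

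**Working it through.** The protocol's only relevant figure is the sample size, 100 to 200 in total, randomised 1:1 (section 4.0). It gives no significance level, power, effect size or SD, so that figure cannot be reproduced. A two-sided 5% test is assumed throughout, with n = 50 or 100 per arm.

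**Step 1. Which data exist at each time point**

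| Weeks from randomisation | Randomised device arm | Randomised observation arm |
|---|---|---|
| 12 | scheduled | scheduled, no device yet |
| 24 | scheduled | crossed over: 12 weeks of device; declined: no visit scheduled |
| 36 | ended | crossed over: 24 weeks of device (12 + 24) |

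Week 12 gives a clean comparison of 50 v 50 or 100 v 100. At an assumed 80% power the detectable standardised difference is (1.96 + 0.84) × √(2/n), which is 0.56 for n = 50 and 0.40 for n = 100. No row after week 12 holds scheduled untreated control data.

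**Step 2. The 24-week contrast by randomised arm**

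Assume a device effect of 0.5 SD, fully gained by crossed-over controls by week 24, and suppose decliners are somehow measured. With crossover share c, the contrast is 0.5 × (1 − c). The power in favour of the device is Φ(contrast × √(n/2) − 1.96).

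| c | Contrast (SD) | n = 50 per arm | n = 100 per arm |
|---|---|---|---|
| 0 | 0.50 | 71% | 94% |
| 0.5 | 0.25 | 24% | 42% |
| 0.8 | 0.10 | 7% | 11% |
| 1.0 | 0 | 2.5% | 2.5% |

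If post-crossover control data are excluded instead, only decliners remain, and they have no scheduled visits.

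**Step 3. What the wording permits if crossed-over controls join the device side**

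The device side becomes n + cn and the usual-care side stays n. The share of the device side that is also counted as usual care is c/(1 + c).

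| c | N = 100 | N = 200 | Shared |
|---|---|---|---|
| 0.5 | 75 v 50 | 150 v 100 | 33% |
| 0.8 | 90 v 50 | 180 v 100 | 44% |
| 1.0 | 100 v 50 | 200 v 100 | 50% |

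At c = 1.0 that is 150 or 300 records from 100 or 200 people.

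**Step 4. Illustrative bias of that pooled contrast**

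Let natural improvement be m1 SD in weeks 0–12 and m2 SD in weeks 12–24, with no device effect. The bias is c/(1 + c) × m2 if crossed-over controls keep the study-entry baseline, and c/(1 + c) × (m2 − m1) if baseline is reset before the device. Take c = 1 and m1 = 0.3, let m2 run from 0 to 0.3, and simulate a two-sample t-test that treats all records as independent (10,000 runs, change-score SD 1):

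- Study-entry baseline (assumed correlation of the two change scores 0.5): bias 0 to +0.15 SD. False positives favouring the device are 0.9% to 8.8% (N = 100) or 1.0% to 18.0% (N = 200), against 2.5% nominal.
- Reset baseline (assumed correlation −0.3): bias −0.15 to 0 SD. Total type I error falls from 15.9% to 7.4% (N = 100) or from 24.9% to 7.4% (N = 200) as m2 rises, against 5% nominal.

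The direction turns on the baseline alone, which section 5.0 does not settle for a crossed-over control.

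**The case against.** The strongest reply is that randomised arms at week 12 is the ordinary reading. Section 4.0 randomises 1:1 to two arms, describes each regimen by randomised allocation, and still calls people control or observation subjects when it offers them the crossover. Section 8.2 speaks of a treatment arm and a usual care arm. Analysis sets and the handling of crossover data are often left to a statistical analysis plan, which may exist and is not shown here.

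Most of this stands. A reader might infer that the protocol prescribes pooling crossed-over controls with the device arm. It does not: no sentence says so, and the pooled contrast has to be assembled from several. The clock from the start of treatment is in the endpoint sentence, not in the null-hypothesis sentence that holds the contrast. A reader might also infer that section 8.2 item 1 and section 8.3 double count patients. They have no control side, so they cannot. Merging the crossover cohort would only change whom they describe.

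What the reply does not answer is the 24-week time point. The protocol itself fixes it in the primary comparison. An analysis plan that kept it would have no scheduled untreated controls to use.

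**Conclusion.** The point holds for 24 weeks, from the protocol's own text and with no numerical assumption: the stated contrast with usual care has no scheduled untreated control there. The week-12 comparison is sound when read as randomised arms, since no control is offered the device before then.

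Double counting is something the wording allows, not something the protocol states it will do. The figures in steps 2 to 4 rest on assumed effect size, crossover share, natural course, correlation and baseline. They show that the 24-week contrast can shrink towards nothing and that a pooled contrast can err in either direction. They do not predict an error rate for this trial, and it would be wrong to read them as showing a bias in favour of the device.

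**What to change.** - **Section 8.1:** define the primary between-arm comparison as participants randomised to Nu-V3 against participants randomised to observation, analysed as randomised, at 12 weeks after randomisation, using data before any crossover. Remove 24 weeks from this comparison.
- **Section 8.2 item 2:** report 24-week change for the randomised device arm only, labelled as uncontrolled within-arm change.
- **Section 4.0:** describe crossed-over controls as a separate open-label crossover cohort. Report it separately and descriptively, with the last pre-device score as baseline, and keep it out of the device-arm summaries in sections 8.2 and 8.3. Align the baseline sentence in section 5.0.

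This is wording only. It needs no extra patients, visits or data, and the offer of crossover is untouched. The cost is that the 24-week result no longer counts as controlled evidence and crossover data no longer enlarge the device group.
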